5.3 DRUG CONCENTRATION MEASUREMENTS AND PHARMACOKINETICS

5.3.1 Assessment of pharmacokinetics

For the assessment of pharmacokinetics, blood samples will be collected at the time points indicated in the [Flow Chart](#). The actual sampling times will be recorded and used for determination of pharmacokinetic parameters.

5.3.2 Methods of sample collection

[figure not shown]
5.3.2.1 Blood sampling for pharmacokinetic analysis

For quantification of BI 1358894 concentrations in plasma, 2.7 mL of blood will be drawn from an antecubital or forearm vein into an K₂-EDTA (dipotassium ethylenediaminetetraacetic acid)-anticoagulant blood drawing tube at the times indicated in the Flow Chart. Blood will be withdrawn by means of either an indwelling venous catheter or by venipuncture with a metal needle.

The EDTA-anticoagulated blood samples will be centrifuged for approximately 10 min at approximately 2000 g to 4000 g and at 4 to 8 °C. Two plasma aliquots will be obtained and stored in polypropylene tubes. The first aliquot should contain at least 0.5 mL of plasma. The process from blood collection until transfer of plasma aliquots into the freezer should be completed within 120 minutes, with interim storage of blood samples and aliquots at room temperature. The time each aliquot was placed in the freezer will be documented. Until transfer on dry ice to the analytical laboratory, the aliquots will be stored upright at approximately -20°C or below at the trial site. The second aliquot will be transferred to the analytical laboratory after the bioanalyst has acknowledged safe arrival of the first aliquot. At the analytical laboratory, the plasma samples will be stored at approximately -20°C or below until analysis.

At a minimum, the sample tube labels should list BI trial number, subject number, visit, and planned sampling time.

After analysis, the plasma samples may be used for further methodological investigations (e.g. for stability testing or assessment of metabolites) or to address Health Authority questions regarding the results/methodology. However, only data related to the analyte and/or its metabolite(s) including anti-drug antibodies (if applicable) will be generated by these additional investigations. The trial samples will be discarded after completion of the additional investigations but not later than 5 years after the CTR is archived.

5.3.4 Pharmacokinetic - pharmacodynamic relationship

No analysis of the relationship between pharmacokinetic and pharmacodynamic parameters is planned for this trial.

5.4 ASSESSMENT OF BIOMARKERS

Not applicable

5.5 BIOBANKING

Not applicable.

5.6 OTHER ASSESSMENTS

5.6.1 Pharmacogenomic evaluation

Pharmacogenomic investigations explore the role of genetic variation in determining an individual's response to drugs. For this purpose, a sample of at most 10 mL of blood will be obtained at the screening examination from each subject whose genotype has not been previously determined. Separate informed consent for genotyping will be obtained from each volunteer prior to sampling.

Deoxyribonucleic acid (DNA) will be extracted from the blood sample in order to sequence genes coding for proteins that are involved in the absorption, distribution, metabolism, and excretion (ADME) of drugs. The gene sequences to be determined include known and likely functional variations of key ADME genes and incorporate more than 90% of ADME-related genetic markers identified by the PharmaADME group (weblink [REDACTED]). It is not intended to include the pharmacogenomic data in the CTR. However, the data may be part of the CTR, if necessary.

5.7 APPROPRIATENESS OF MEASUREMENTS

All measurements performed during this trial are standard measurements and will be performed in order to monitor subjects' safety and to determine pharmacokinetic parameters in an appropriate way.

The scheduled measurements will allow monitoring of changes in vital signs and standard laboratory values that might occur as a result of administration of trial medication. The safety

Proprietary confidential information © 2022 Boehringer Ingelheim International GmbH or one or more of its affiliated companies

assessments are standard, are accepted for evaluation of safety and tolerability of an orally administered drug, and are widely used in clinical trials. The pharmacokinetic parameters and measurements outlined in Section [5.3](#) are generally used assessments of drug exposure. Prospective suicidality assessment is performed in this trial using the recommended C-SSRS questionnaire [[R08-1147](#), [R12-4395](#)]

6. INVESTIGATIONAL PLAN

6.1 VISIT SCHEDULE

Exact times of measurements outside the permitted time windows will be documented. The acceptable time windows for screening and the end of trial examination are provided in the [Flow Chart](#).

Study measurements and assessments scheduled to occur 'before' trial medication administration on Day 1 are to be performed and completed within a 3 h-period prior to the trial drug administration.

Up to 48 h after drug administration (planned time), the acceptable deviation from the scheduled time for adverse event/concomitant medication questioning, suicidality assessment, vital signs, ECG, and laboratory tests will be \pm 30 min, if not stated otherwise in the Flow Chart,

For PK sampling, no time window is defined for this period (i.e. up to 48 h after drug administration).

Starting from planned time of 48 hours after drug administration (and beyond) a time window of \pm 120 minutes will be allowed for all procedures

Starting from a planned time of 168 hours after drug administration (and beyond) a time window of \pm 26 hours will be allowed for all procedures

If scheduled in the Flow Chart at the same time as a meal, blood sampling, vital signs, and 12-lead ECG recordings have to be done first. Furthermore, if several measurements including venipuncture are scheduled for the same time, venipuncture should be the last of the measurements due to its inconvenience to the subject and possible influence on physiological parameters.

For planned blood sampling times, refer to the Flow Chart. While these nominal times should be adhered to as closely as possible, the actual sampling times will be recorded and used for the determination of pharmacokinetic parameters.

If a subject misses an appointment, it will be rescheduled if possible. The relevance of measurements outside the permitted time windows will be assessed no later than at the Report Planning Meeting.

6.2 DETAILS OF TRIAL PROCEDURES AT SELECTED VISITS

6.2.1 Screening

After having been informed about the trial, all subjects will provide written informed consent in accordance with GCP and local legislation prior to enrolment in the trial.

For information regarding laboratory tests (including drug and virus screening), ECG, vital signs, suicidality assessment, and physical examination, refer to Sections [5.2.1](#) to [5.2.5](#).

Genotyping will be performed in those volunteers whose genotypes have not been previously determined (for details, see Section [5.6](#)).

Proprietary confidential information © 2022 Boehringer Ingelheim International GmbH or one or more of its affiliated companies

At Screening, adequate contraceptive measures are described and the background why strict adherence to the measures is required.

It must be reiterated, at all visits following a screening, that WOCBP are using the appropriate method of safe contraception pursuant to section 4.2.2.3.

6.2.2 Treatment period

Each subject is expected to participate in 4 treatment periods (each consisting of Days -1, 1-7, 11 and 14 in each period). At least 17 days will separate drug administrations in the first, second, third and fourth treatment period.

In the evening of Day -1 of each treatment period, trial participants will be admitted to the trial site and kept under close medical surveillance for at least 24 hours following drug administration. The subjects will then be allowed to leave the trial site after formal assessment and confirmation of their fitness. On all other trial days, subjects will be treated in an ambulatory fashion.

For details on time points and procedures for collection of plasma samples for PK analysis, refer to [Flow Chart](#) and Section [5.3.2](#).

The safety measurements performed during the treatment period are specified in Section [5.2](#) of this protocol and in the Flow Chart. AEs and concomitant therapy will be assessed continuously from obtaining subject's written informed consent until the end of trial examination. For details on times of all other trial procedures, refer to the Flow Chart.

6.2.3 Follow-up period and trial completion

For AE assessment, laboratory tests, suicidality assessment, recording of ECG and vital signs, and physical examination during the follow-up period, see Section 5.2.

Subjects who discontinue treatment before the end of the planned treatment period should undergo the EoS Visit.

If needed in the opinion of the investigator, additional visits may be scheduled after the EoS Visit for continued safety monitoring.

All abnormal values (including laboratory parameters) that are assessed as clinically relevant by the investigator will be monitored using the appropriate tests until a return to a medically acceptable level is achieved. (S)AEs persisting after a subject's EoS Visit must be followed until they have resolved, have been sufficiently characterised, or no further information can be obtained.

7. STATISTICAL METHODS AND DETERMINATION OF SAMPLE SIZE

7.1 NULL AND ALTERNATIVE HYPOTHESES

The relative bioavailability of the interested treatment comparisons:

- i) T_{fasted} versus R_{fasted}
- ii) T_{fed} versus R_{fed}
- iii) T_{fed} versus T_{fasted}
- iv) R_{fed} versus R_{fasted}

will be estimated by the ratios of the geometric means (treatment A/treatment B, with A, B representing first, respectively second treatment of each pairwise comparisons stated above), and their corresponding 2-sided 90% confidence intervals (CIs) will be provided. This method corresponds to the two one-sided t-test procedure, each at the 5% significance level. Since the main focus is on estimation and not testing, a formal hypothesis test and associated acceptance range is not specified.

Due to the exploratory nature of the assessment, no significance level adjustment for investigating multiple comparisons will be applied.

7.2 PLANNED ANALYSES

7.2.1 General considerations

7.2.1.1 Analysis sets

Statistical analyses will be based on the following analysis sets:

- Treated set (TS): The treated set includes all subjects who were treated with at least one dose of trial drug. The treated set will be used for safety analyses.
- Pharmacokinetic parameter analysis set (PKS): This set includes all subjects in the treated set (TS) who provide at least one PK endpoint that was defined as primary or secondary and was not excluded due to a protocol deviation relevant to the evaluation of PK or due to PK non-evaluability (as specified in the following subsection 'Pharmacokinetics'). Thus, a subject will be included in the PKS, even if he/she contributes only one PK parameter value for one period to the statistical assessment. Descriptive and model-based analyses of PK parameters will be based on the PKS.

Descriptions of additional analysis sets may be provided in the TSAP.

Adherence to the protocol will be assessed by the trial team. Important protocol deviation (iPD) categories will be suggested in the iPD specification file. IPDs will be identified no later than in the Report Planning Meeting, and the iPD categories will be updated as needed.

7.2.1.2 Pharmacokinetics

The pharmacokinetic parameters listed in Section [2.1](#) and [2.2.2](#) for drug BI 1358894 will be calculated according to the relevant BI internal procedures.

Plasma concentration data and parameters of a subject will be included in the statistical pharmacokinetic (PK) analyses if they are not flagged for exclusion due to a protocol deviation relevant to the evaluation of PK (to be decided no later than in the Report Planning Meeting) or due to PK non-evaluability (as revealed during data analysis, based on the criteria specified below). Exclusion of a subject's data will be documented in the CTR.

Important protocol deviations may be

- Incorrect trial medication taken, i.e. the subject received at least one dose of trial medication the subject was not assigned to
- Incorrect dose of trial medication taken
- Incorrect intake of meal prior to drug administration in treatment periods under fed condition
- Use of restricted medications

Plasma concentrations and/or parameters of a subject will be considered as non-evaluable, if for example

- The subject experienced emesis that occurred at or before two times median t_{max} of the respective treatment (Median t_{max} is to be determined excluding the subjects experiencing emesis),
- A BI 1358894 predose concentration is $>5\% C_{max}$ value for a subject for a specific treatment period, that specific treatment period will be excluded
- Missing samples/concentration data at important phases of PK disposition curve

Plasma concentration data and parameters of a subject which are flagged for exclusion will be reported with its individual values but will not be included in the statistical analyses.

Descriptive and inferential statistics of PK parameters will be based on the PKS.

Only concentration values within the validated concentration range and actual sampling times will be used for the calculation of pharmacokinetic parameters. Concentrations used in the pharmacokinetic calculations will be in the same format provided in the bioanalytical report, (that is, to the same number of decimal places provided in the bioanalytical report).

7.2.2 Primary endpoint analyses

Primary analyses

The statistical model used for the analysis of the primary endpoints will be an analysis of variance (ANOVA) model on the logarithmic scale. That is, the PK endpoints will be log-transformed (natural logarithm) prior to fitting the ANOVA model. This model will include effects accounting for the following sources of variation: sequence, subjects within sequences, period and treatment.

Proprietary confidential information © 2022 Boehringer Ingelheim International GmbH or one or more of its affiliated companies

The effect 'subjects within sequences' will be considered as random, whereas the other effects will be considered as fixed. The model is described by the following equation:

$$y_{ijkm} = \mu + \zeta_i + s_{im} + \pi_j + \tau_k + e_{ijkm}, \text{ where}$$

y_{ijkm} = logarithm of response measured on subject m in sequence i receiving treatment k in period j,

μ = the overall mean,

ζ_i = the i^{th} sequence effect, $i = 1, 2, 3, 4$

s_{im} = the effect associated with the m^{th} subject in the i^{th} sequence,
 $m = 1, 2, \dots, 6$

π_j = the j^{th} period effect, $j = 1, 2, 3, 4$

τ_k = the k^{th} treatment effect, $k = 1, 2, 3, 4$

e_{ijkm} = the random error associated with the m^{th} subject in sequence i who received treatment k in period j.

where $s_{im} \sim N(0, \sigma_B^2)$ i.i.d., $e_{ijkm} \sim N(0, \sigma_W^2)$ i.i.d. and s_{im} , e_{ijkm} are independent random variables.

Point estimates for the ratios of the geometric means (treatment A / treatment B) for the comparisons as stated in Section [7.1](#) and the primary endpoints (see Section [2.1](#)) with their two-sided 90% confidence intervals (CIs) will be provided.

For each endpoint, the difference between the expected means for $\log(A)$ - $\log(B)$ will be estimated by the difference in the corresponding adjusted means (Least Squares Means). Additionally, their two-sided 90% confidence intervals will be calculated based on the residual error from the ANOVA and quantiles from the t-distribution. These quantities will then be back-transformed to the original scale to provide the point estimate and 90% CIs for each endpoint.

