7.5 DETERMINATION OF SAMPLE SIZE

It is planned to enter a total of 24 subjects in the trial including up to 4 drop-outs. The sample size is considered sufficient to achieve the aims of this exploratory trial. With this sample size, the following precision in estimating the ratio of geometric means (treatment A/treatment B; with A, B representing respective treatments of the pairwise treatment comparisons of interest, see Section [7.1](#)) can be expected with 95% probability. Precision is defined as the ratio of upper CI limit (CL) to the relative BA estimate. Note that the precision is independent of the actual ratio of geometric means.

The observed intra-individual coefficient of variation (gCV) for BI 1358894 TFII in previous trial (1402-0010 [[c28907328](#)]) was roughly 25% for C_{max} and 13% for AUC.

Proprietary confidential information © 2022 Boehringer Ingelheim International GmbH or one or more of its affiliated companies

For various assumptions around the gCV of 15-25%, Table 7.5: 1 provides an overview of the achievable precision for estimating the ratio of geometric means (treatment A/treatment B) for the formulation differences, i.e. comparisons i) and ii) (see Section 7.1). Table 7.5: 2 provides an overview of the achievable precision for estimating the food effect of each formulation, i.e. comparisons iii) and iv) (see Section 7.1), [REDACTED]

[REDACTED]. For illustrative purposes, the expected 90% confidence intervals are displayed for different values of the ratios A/B of geometric means. Note, as the same intra-individual gCVs and sample sizes N are assumed for the assessment of formulation differences and food effect, the precisions in Table 7.5.1 and 7.5.2 are the same, only different ratios are expected and are displayed with the respective 90% CI in the tables below.

Table 7.5: 1

Precision that can be expected with 95% probability and illustrative two-sided 90% confidence intervals around the ratios of geometric means (A/B) for different gCVs in a 4x4 crossover trial ($N=20, 24$) assessing formulation differences

N	gCV [%]	Precision upper CL** / relative BA estimate	90% CI [%] of respective ratio*		
			90	100	110
20	15	1.10	(82.15; 98.60)	(91.23; 109.56)	(100.41; 120.51)
	20	1.13	(79.73; 101.59)	(88.59; 112.88)	(97.45; 124.17)
	25	1.16	(77.42; 104.63)	(86.02; 110.44)	(94.62; 127.88)
24	15	1.09	(82.92; 97.69)	(92.13; 108.54)	(101.34; 119.40)
	20	1.12	(80.72; 100.35)	(89.69; 111.50)	(98.66; 122.65)

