## 7. PLANNED ANALYSIS

Safety analysis (refer to [Section 7.8](#)) will be performed by the [REDACTED] and will be presented in Sections 15.1 to 15.4 of the CTR and in Appendix 16.2 and 16.1.13.1.

Inferential statistical analyses of PK endpoints (refer to [Section 7.4](#) and [Section 7.5.2](#)) will also be performed by the [REDACTED] and will be presented in Section 15.5 of the CTR and in Appendix 16.1.13.3.

Descriptive data analysis of PK endpoints and concentrations will be performed by the [REDACTED] and will be presented in Section 15.6 of the CTR and in Appendix 16.1.13.3.

The format of the listings and tables will follow the BI standards (see “Standards for Reporting of Clinical Trials and Project Summaries” ([6](#)) with the exception of those generated for PK-calculations following BI standards for PK/PD analysis ([7](#)).

The individual values of all subjects will be listed, sorted by treatment sequence, subject number and visit, except for listings regarding PK, which will be sorted by treatment, subject number and planned time. The listings will be included in Appendix 16.2 and for PK in Appendix 16.1.13 of the CTR.

For end-of-text tables, the set of summary statistics for non-PK parameters is:

N	number non-missing observations
Mean	arithmetic mean
SD	standard deviation
Min	minimum
Median	median
Max	maximum

For analyte concentrations, the following descriptive statistics will additionally be calculated:

CV	arithmetic coefficient of variation
gMean	geometric mean
gCV	geometric coefficient of variation

For PK parameters, the following descriptive statistics will additionally be calculated:

P10	10 th percentile
Q1	1 st quartile
Q3	3 rd quartile
P90	90 th percentile

The descriptive statistics of concentrations will be displayed with three significant digits. The descriptive statistics of PK parameters will be calculated using the individual values with the number of decimal places as provided by the evaluation program. Then the individual values as well as the descriptive statistics will be reported with three significant digits in the CTR.

Tabulations of frequencies for categorical data will include all possible categories and will display the number of observations in a category as well as the percentage (%) relative to the respective treatment group (unless otherwise specified, all subjects in the respective subject set whether they have non-missing values or not).

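### Should the 90% confidence intervals rest on one residual variance pooled over all four treatments?

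*Protocol*

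**What the plan says.** Protocol 7.1 names four comparisons: T against R fasted, T against R fed, and fed against fasted for each formulation. For each ratio of geometric means, "their corresponding 2-sided 90% confidence intervals (CIs) will be provided". Protocol 7.2.2 fits one ANOVA with sequence, subject within sequence, period and treatment, and with a single within-subject variance for all observations. From this model, "two-sided 90% confidence intervals will be calculated based on the residual error from the ANOVA and quantiles from the t-distribution". SAP 7.4.1 reproduces the model, and SAP 4 announces no change to the planned analyses.

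The planning rests on the same assumption and says so. Protocol 7.5 explains that the two precision tables share their precision values, "as the same intra-individual gCVs and sample sizes N are assumed for the assessment of formulation differences and food effect".

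The inferential status is also explicit. Protocol 7.1 states: "Since the main focus is on estimation and not testing, a formal hypothesis test and associated acceptance range is not specified". It calls the assessment exploratory, and "no significance level adjustment for investigating multiple comparisons will be applied".

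**The concern.** One residual sets the width of four intervals that answer two different questions. The formulation comparison in the fasted state needs only the variance of the fasted periods, and the fed comparison only that of the fed periods. Food can change the variability of absorption as well as its mean, and the size of a food effect can differ between subjects. Either would make some pooled intervals too narrow and others too wide, so the error would not be uniformly conservative.

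The ratios and their 90% intervals are the trial's main result. Neither Protocol 7.2.2 nor SAP 7.4.1 contains a pairwise fit, a variance by treatment or another model that relaxes the assumption. A short supportive analysis, refitting the model to the two treatments of each comparison, looks cheap to add before the data are seen.

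**Working it through.** **Inputs.** From Protocol 7.5: 24 subjects with up to 4 drop-outs; a previous intra-individual gCV for TFII of about 25% for Cmax and 13% for AUC; planning range 15–25%. From 7.2.2: one residual variance. The sequences are in a figure that is not shown, so a Williams square is assumed. The visible text gives no gCV by food state or for iCF, so every split below is an assumption.

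**1. The plan's own figure.** With σ² = ln(1 + gCV²) and residual df = 3N − 6, the log half-width reached with 95% probability is

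t(0.95, df) × σ × √(2/N) × √(χ²(0.95, df)/df).

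For N = 24 and gCV 25%: σ = 0.2462, df = 66, and 1.668 × 0.2462 × 0.2887 × √(85.96/66) = 0.1353. Table 7.5: 1 prints a lower limit of 87.34 for a ratio of 100, and ln(100/87.34) = 0.1354. For N = 20 (54 df) the formula gives 0.1506, and ln(100/86.02) = 0.1506. So planning and analysis use the same pooled residual.

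**2. Variance differs by food state.** With balanced, complete data the pooled variance averages the fasted and fed variances. A formulation interval then covers with probability of about P(|t66| < 1.668 × pooled SD / correct SD). At 25% fasted and 20% fed:

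- pooled SD = √((0.2462² + 0.1980²)/2) = 0.2234
- fasted: 0.2234/0.2462 = 0.907; 1.668 × 0.907 = 1.513; coverage 86.5%
- fed: 0.2234/0.1980 = 1.128; 1.668 × 1.128 = 1.882; coverage 93.6%
- food effect: twice the pooled variance equals the fasted plus the fed variance, so coverage stays at 90%

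Simulation of the full model (N = 24, 200,000 runs) gives the same values, and these for other splits:

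| Fasted / fed gCV | T/R fasted | T/R fed |
|---|---|---|
| 25 / 22.5% | 88.3% | 91.7% |
| 13 / 12% | 88.7% | 91.4% |
| 25 / 20% | 86.5% | 93.6% |
| 13 / 18% | 95.1% | 85.0% |

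In interval terms, take the 25/20% case, a ratio of 100 and each SD at its expected value. The pooled half-width is 1.668 × 0.2234 × 0.2887 = 0.1076, an interval of 89.8 to 111.4. A two-treatment fit with 21 df gives 1.721 × 0.2462 × 0.2887 = 0.1223 fasted (88.5 to 113.0) and 1.721 × 0.1980 × 0.2887 = 0.0984 fed (90.6 to 110.3).

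**3. Variance differs by formulation.** The same arithmetic applies with the roles exchanged. At T 20% and R 25%, the food interval covers about 93.6% for T and 86.5% for R, and both formulation intervals keep 90%. The assumption therefore concerns all four treatments, not food state alone.

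**4. The food effect varies between subjects.** A log-SD sF adds sF²/3 to the residual mean square. The model then uses 2σ² + (2/3)sF² as the contrast variance, where the truth is 2σ² + sF² for food and 2σ² for formulation. At gCV 13% (σ² = 0.01676) and sF = 0.10:

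- used: 0.0335 + 0.0067 = 0.0402
- food: √(0.0402/0.0435) = 0.961; coverage 88.6%
- formulation: √(0.0402/0.0335) = 1.095; coverage about 92.8%

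At gCV 25%, sF = 0.10 gives 89.6% and 90.9%, close to nominal. A subject-by-formulation interaction does the reverse.

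**5. What the two-treatment fits cost.** They cover 89.9–90.1% in all eight simulated scenarios. Residual df fall from 66 to 20–21 (N = 24) or from 54 to 16–17 (N = 20). At gCV 25% and 95% probability:

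| N | Pooled log half-width | Two-treatment log half-width | Precision |
|---|---|---|---|
| 24 | 0.135 | 0.152–0.154 | 1.15 to 1.16–1.17 |
| 20 | 0.151 | 0.172–0.174 | 1.16 to 1.19 |

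If the variances are equal, the average widening is about 2–3%. The residual gCVs from these fits would be a poor diagnostic: with 21 df each, a two-sided 10% F test detects 25/20% about 25% of the time, and the two estimates come out in the wrong order about 16% of the time.

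**The case for a change.** The strongest case for a change is that in an estimation trial the intervals are the product. One paragraph in the SAP and four extra fits per primary endpoint would give intervals that need neither equal variances nor a constant food effect. Table 7.5: 2 illustrates food ratios up to 180, so the plan itself contemplates a large food effect. Fixing the supportive fit in advance would also avoid a choice made after seeing the data.

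The arithmetic behind this stands: the assumption is real, and the pairwise fits do hold their level. It does not amount to a defect. A large mean food effect is not evidence of unequal variance or of a varying effect. The supportive fits would leave interpretation with the joint ANOVA, so they would change no conclusion, and at this sample size they could not reliably show whether the assumption had failed. They would also drop subjects whom the plan means to keep, since Protocol 7.2.1.1 says "a subject will be included in the PKS, even if he/she contributes only one PK parameter value for one period to the statistical assessment".

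Individual values will be listed in any case (SAP 7 sets the order of its listings, "except for listings regarding PK, which will be sorted by treatment, subject number and planned time"), so a reader who doubts the pooling can derive pairwise intervals. Protocol 7.2.4, SAP 6.4, 7.6 and 10, and some text in Protocol 7.5 beside the food comparisons are not visible, and a check may already stand there.

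**Conclusion.** No change follows. The pooled residual is a legitimate primary model, stated consistently in both documents and matched by the sample-size calculation. It buys 66 residual degrees of freedom instead of 20 or 21 and uses every subject in the PK set. The price is some loss of calibration if the four treatments do not share one within-subject variance, or if the food or formulation effect varies between subjects.

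Under the assumed splits that price runs from under two percentage points of coverage (25/22.5% or 13/12%) to about five (13/18%), always around point estimates that do not move. These figures rest on complete data, 24 subjects and a Williams square. Nothing visible shows that any of the splits applies, and no decision rule depends on interval width. A sponsor who likes the pairwise display may add it, but statisticians reasonably differ on this trade-off and the plan is sound without it.
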